2.7 Rationale for Public Health Emergency mitigation procedures

During a Public Health emergency as declared by Local or Regional authorities i.e. pandemic, epidemic or natural disaster, mitigation procedures to ensure participant safety and trial integrity are listed in relevant sections. Notification of the Public health emergency should be discussed with Novartis prior to implementation of mitigation procedures, and permitted/approved by Local or Regional Health Authorities and Ethics Committees as appropriate.

[figure not shown]
[REDACTED]

3 Objectives and endpoints

Objectives and related endpoints are described in [Table 3-1](#) below.

Table 3-1 Objectives and related endpoints

Objective	Endpoint	Analysis
Primary		Refer to Section 10.4
To determine the MTD and/or RD of the combination of VAY736 with ibrutinib	Safety Escalation only: 
Incidence of DLTs in cycle 1 (28 days) Escalation and expansion: 
Incidence and severity of AEs and SAEs, including changes in laboratory parameters and vital signs Tolerability Dose interruptions, reduction, and dose intensity	
To characterize the safety and tolerability of the combination of VAY736 and ibrutinib		Refer to Section 10.5
Secondary		
To assess any preliminary antitumor activity of the combination	Rate of patients with CR as assessed by investigators per IWCLL at cycle 9 day 1 Overall response rate (ORR) assessed by investigators per IWCLL criteria and Time To Progression (TTP) Clearance of ibrutinib resistance mutations (BTKC481 and/or PLC γ 2 hotspot), defined as less than 1% mutation bearing alleles (Arm B only).	
To characterize the PK of VAY736 and ibrutinib when used in combination therapy	Plasma concentration of VAY736 and ibrutinib, and derived parameters	
To assess immunogenicity (IG) following one or more intravenous infusions of VAY736	Presence of anti-VAY736 antibodies	

Objective	Endpoint	Analysis

[figure not shown]
4 Study design

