7.1 Study flow and visit schedule

Table 7-1 and Table 7-2 list all of the assessments and indicate with an “X”, the visits when they are performed. Unscheduled testing may be conducted as necessary to address safety concerns. All data obtained from these assessments must be supported in the patient’s source documentation. The table indicates which assessment produce data to be entered into the database (D) or remain in source documentation only (S) (Category column). No CRF will be used as a source document.

C1D1 assessments can be conducted within 3 days prior to C1D1. On treatment assessments can be conducted within 3 days prior to the planned assessment. If screening assessments are conducted within 3 days of C1D1, they do not need to be repeated for C1D1.

After C1D1, tests and/or procedures should occur on schedule whenever possible. A visit window of +/- 3 days is allowed for assessments except imaging and PK. For PK samples, with the exception of collection(s) made on Day 1 (corresponding with dosing), if PK assessment must be delayed for scheduling purposes, it is mandatory that the correct date and time of the collection are captured in the eCRF. On PK collection days, the time windows are provided in [Table 7-6](#), [Table 7-7](#), and [Table 7-8](#). In situations when dosing is delayed, PK collections should also be delayed until the subsequent dose is given. See [Section 7.2.1](#) for windows on imaging.

Table 7-1 Visit evaluation schedule for Q2W VAY736 dosing regimen

	Category	Protocol Section	Screening	Cycle 1		Cycle 2		Cycle 3		Cycle 4		Subsequent cycles		End of study treatment (EoT)	30-day Follow up	TTP	
				1	2	4	8	15	1	15	1	2	4	8	15	1	15
Day of cycle																	
Obtain Informed Consent	D	7.1.1.1	X														
Demography	D	7.1.1.2	X														
Inclusion/exclusion criteria	D	5	X														
Relevant medical history/current medical conditions	D	7.1.1.2	X														
Diagnosis and extent of cancer	D	7.1.1.2	X														
Prior antineoplastic therapy	D	7.1.1.2	X														
Antineoplastic therapies since discontinuation of study treatment	D	7.1.2														X	X
Prior/concomitant medications	D	7.1.1.2	X													Continuous	

Physical examination	S	7.2.2.1	X	X			X	X		X			X		X (Q3M after C9)			
Performance status	D	7.2.2.4	X	X				X		X			X		X (Q3M after C9)		X	
Height	D	7.2.2.3	X															
Weight	D	7.2.2.3	X	X			X	X		X			X		X (through C6 or through C8 if continuing VAY736 treatment)			

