7.2.2.6 Cardiac assessments

7.2.2.6.1 Electrocardiogram (ECG)

A standard 12 lead ECG will be performed in accordance with institutional practice for patients at screening, end of treatment, and as clinically indicated.

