7.2.3.1 Pharmacokinetics and immunogenicity blood sample collection and handling

If the dosing of Cycle 3 Day 1 for VAY736 or Cycle 1 Day 8 for ibrutinib is delayed, the PK sampling for the full PK profile should be delayed until the dose of VAY736 or ibrutinib is administered. On the date of administration, the PK samples should be collected to match the scheduled time points for Cycle 3 as outlined in [Table 7-6](#) or [Table 7-7](#) for VAY736 or Cycle 1 in [Table 7-8](#) for ibrutinib.

Exact dates and actual PK blood draw times will be recorded on the appropriate eCRF. Any sampling problems (e.g. patient administrated with study drug before the PK blood draw took place) must be noted in the comments section of the eCRF and on appropriate source documentation.

If any of the scheduled sampling times are missed or a sample is not drawn according to this schedule, the actual collection date and time will be recorded and the remaining samples will be collected on schedule whenever possible.

If vomiting occurs within 8 hours following ibrutinib administration on the day of PK sampling, where post-dose time-points are collected, no additional study medication should be taken in an effort to replace the material that has been vomited. The time (using the 24-hour clock) of vomiting should be recorded in the Adverse Events eCRF.

Unscheduled PK samples should be collected if any of the following events occur:

- If a patient treated with investigational drugs experiences an AE that results in an unscheduled visit or fits the criteria of a SAE or DLT, as determined by the investigator.
- Whenever an ECG with a QTcF change from baseline > 60 ms or a new absolute QTcF ≥ 501 ms result is known. The exact time of sample collection should be noted in the unscheduled eCRF.
- In the event of other clinically significant AEs (such as infusion reaction/anaphylaxis) or if immunogenicity is suspected.
- During safety follow-up period either at or prior to end of safety follow-up period

Residual PK and IG serum or plasma samples used for PK and IG analysis may also be used for [REDACTED] metabolites and/or PD analyses related to VAY736 or ibrutinib therapy and cancer. If conducted, these results will be reported separately.

Refer to the [VAY736Y2102 Laboratory Manual] for detailed instructions for the collection, handling, and shipment of PK and immunogenicity samples.

Table 7-6 Pharmacokinetic blood collection log for VAY736 Q2W dosing (VAY736, IG, [REDACTED])

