10.4.1 Variable

- Incidence and severity of adverse events (AEs) and serious adverse events (SAEs)
- Changes in laboratory parameters, vital signs, and electrocardiograms (ECGs)
- Incidence of DLTs during the first treatment cycle (escalation only)
- Dose interruptions, reductions and dose intensity

Estimation of the MTD in the dose-escalation part of the study will be based upon the estimation of the probability of DLT in Cycle 1 for patients in the dose-determining set. This probability is estimated by the statistical models in [Section 10.4.2](#).

A dose-limiting toxicity (DLT) is defined as an adverse event or abnormal laboratory value assessed as clinically relevant, occurring \leq 28 days following the first administration of study treatment as defined in [Section 6.2.4, Table 6-3](#).

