10.5.3.4 Other safety data

ECG

- Listing of ECG evaluations for all patients with at least one abnormality

Vital signs

Data on vital signs will be tabulated and listed, notable values will be flagged.

- Shift table baseline to worst on-treatment result
- Table with descriptive statistics at baseline, one or several post-baseline time points and change from baseline to this/these post-baseline time points

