 - In SAP, after discussions with clinical and PKS line functions, we have updated this to vomiting within 4 hours of ibrutinib administration. The eCRF was not per-protocol for unknown reasons and instead collected vomiting with 4 hours of dosing. PKS confirmed that 4 hours of monitoring should be sufficient for ibrutinib based on Tmax half-life and standards.
- 7. In Protocol v06, Section 10.1.4, the definition of the Dose-determining analysis set (DDS) includes patients from the FAS from both the expansion and escalation parts of the study.
 - In SAP, patients from the expansion parts of the study will not be included as part of the definition of the DDS to align with Section 6.2.4 and Section 10.4.1 in the Protocol which clearly specify that DLTs will be reported for the escalation part of the study.
- 8. In Protocol v06, Section 10.4.1, changes in electrocardiograms are considered as part of the primary objective.
 - In SAP, reference to ECG monitoring and analysis as part of the primary objective was removed to align with Table 3-1 Objectives and related endpoints of the Protocol.
- 9. In Protocol v06, Section 10.5.3.4 a listing of ECG evaluations for all patients with at least one abnormality should be presented.
 - In SAP, as ECG is not considered part of the study objectives, no ECG data will be listed.

5 Appendix

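### SAP Section 4 item 9 withdraws the only ECG output the protocol plans, for a reason that does not cover it; the abnormal-ECG listing should be restored

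*SAP*

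**What the plan says.** Protocol 7.2.2.6.1 sets the schedule: "A standard 12 lead ECG will be performed in accordance with institutional practice for patients at screening, end of treatment, and as clinically indicated". That section falls under 7.2.2, safety and tolerability assessments.

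The protocol is not consistent about the status of these ECGs. Section 10.4.1 includes among the variables for the primary objective "Changes in laboratory parameters, vital signs, and electrocardiograms (ECGs". Table 3-1 gives the corresponding endpoint as "Incidence and severity of AEs and SAEs, including changes in laboratory parameters and vital signs", without ECG.

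For output, protocol 10.5.3.4 (Other safety data) plans one item: "Listing of ECG evaluations for all patients with at least one abnormality".

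SAP Section 4 declares two changes. In item 8, "reference to ECG monitoring and analysis as part of the primary objective was removed to align with Table 3-1". Item 9 then disposes of the listing: "In SAP, as ECG is not considered part of the study objectives, no ECG data will be listed". SAP 2.8.3, the section on other safety data, accordingly contains only vital signs. Two traces of ECG remain elsewhere in the SAP. Section 2.6 refers safety and tolerability analysis to protocol 10.5.3 as a whole, and the baseline rule in 2.1.1.4 still covers ECG values.

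**The concern.** Item 9 goes further than item 8. Item 8 settles whether ECG is a primary endpoint. Item 9 treats that as settling whether ECG data are reported at all. These are separate questions: a safety listing does not need primary-endpoint status to be produced, and protocol 10.5.3.4 did not make it depend on that.

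At stake are ECG abnormalities that were recorded but not entered as AEs. Cardiac findings matter for this combination. Protocol 1.2.4.1.2 names atrial fibrillation among the reactions that led to ibrutinib discontinuation (1%), exclusion criterion 13 screens out patients with risk factors for Torsades de Pointes, Table 6-5 prescribes repeat ECGs after certain ECG changes, and protocol 1.3.2 reports no clinical data on the combination. A reader of the study report would expect to be able to see which patients had an abnormal ECG.

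**Working it through.** No arithmetic is involved beyond a count of outputs. The check sets the sections side by side.

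**1. Does the stated reason cover the listing?**
- The primary objective in both documents includes characterizing safety and tolerability (protocol Table 3-1 and 10.4; SAP Table 1-1 and 2.6). ECG is a safety assessment by its place in protocol 7.2.2.6.
- Table 3-1 introduces laboratory parameters and vital signs with the word *including*. It does not say that other safety data fall outside the objective.
- Aligning 10.4.1 with Table 3-1 therefore supports item 8. It does not reach 10.5.3.4, which is a separate provision for other safety data.

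**2. Is the SAP consistent with itself?**
- SAP 2.6 points to protocol 10.5.3 for safety analysis. Protocol 10.5.3.4 is part of that section and contains the listing.
- SAP Section 4 item 9 says that there will be no listing. A programmer following 2.6 and one following item 9 would produce different outputs.

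**3. What is still reported without item 9's listing?**

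| Data | Named in protocol Table 3-1 | Planned in protocol 10.5.3 | Planned in the SAP, independent of AE reporting |
|---|---|---|---|
| Laboratory | Yes | Listing, worst grade, shift tables (10.5.3.3) | Shift tables; listing of grade 3 or 4 values (2.8.2.3.1) |
| Vital signs | Yes | Tables and listing, notable values flagged (10.5.3.4) | Number and percentage of patients with notable values (2.8.3.1) |
| ECG | No | Listing for patients with an abnormality (10.5.3.4) | None |

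Under protocol 8.1.1, an abnormal test result becomes an AE only if it causes signs or symptoms, is judged clinically significant, or needs therapy or a change in study medication. ECG findings that meet this test and are recorded go into the AE listing and, if treatment-emergent, the AE tables (SAP 2.8.2.1.2). ECG abnormalities that do not meet it, or were not entered, appear nowhere.

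**4. Count of ECG-specific outputs.**
- Abnormality listing: 1 in the protocol, 0 in the SAP.
- QTcF or change-from-baseline summary: 0 in the protocol, 0 in the SAP.

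**5. Are the data there to list?** Protocol 7.1 explains that category D in the visit tables marks data for the database, and the ECG row in Table 7-2 (Q4W schedule) carries D. I could not read an ECG row in Table 7-1 (Q2W schedule) in the copy available to me. I assume that it has the same category, since 7.2.2.6.1 does not distinguish between regimens.

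**The case against.** The case for the SAP has real substance.

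- **The protocol conflict is genuine.** Only 10.4.1 names ECG for the primary objective. Table 3-1, the protocol summary and the opening of 7.2.2 name laboratory measures and vital signs but not ECG. Resolving this in favour of the objectives table is defensible, so item 8 stands.
- **The change is open.** It is declared in the section meant for such changes and identifies the protocol section concerned. One can argue that the specific statement in item 9 overrides the general cross-reference in 2.6. That tells a programmer what to do, but it does not supply the missing reason.
- **AE reporting catches what matters most.** A clinically significant arrhythmia recorded as an AE will be reported. This stands, and it limits the size of the point.
- **The ECG data are sparse.** ECGs are scheduled only at screening and end of treatment, plus any that are clinically indicated. There is no control arm, and patients enter already taking ibrutinib. This argues against building summary tables, but not against a listing of abnormal cases.

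A reader might infer that collected QTcF and rhythm data will never be reported. The documents do not support that. QTcF appears only as a trigger for an unscheduled PK sample ("Whenever an ECG with a QTcF change from baseline > 60 ms", or a new absolute value of at least 501 ms, protocol 7.2.3.1). Nothing shows which ECG fields the eCRF holds, and the protocol never planned a QTcF summary. Nor does it follow that PK samples triggered by QTcF can no longer be traced to their ECG, since leaving out a listing deletes no records.

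**Conclusion.** The point holds in a limited form. Item 9 removes the single ECG output that the protocol planned, and the reason given justifies only item 8. The effect is that ECG abnormalities not reported as AEs appear in no planned output, although non-AE laboratory and vital-sign abnormalities are still shown.

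The size in patients is unknown. Protocol Amendment 06 gives 15 patients enrolled in escalation and 11 on treatment in expansion, but these are status figures at that date and not the final denominator, and the documents give no count of abnormal ECGs. Patients whose ECGs were all normal would not have been listed under the protocol either.

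One might go further and say that the SAP wrongly demoted a primary safety variable, or that the report could say nothing about cardiac rhythm. Neither follows: 10.4.1 stands alone against Table 3-1, and recorded cardiac AEs remain in the report.

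The conclusion assumes that ECG results, or at least the finding of an abnormality, are in the database for both dosing schedules.

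**What to change.** Delete item 9 from SAP Section 4 and restore the abnormal-ECG listing of protocol 10.5.3.4 under SAP 2.8.3 as other safety data. SAP 2.6 and 2.1.1.4 then need no change, and item 8 may stand. SAP Section 1 provides the route: an amendment before database lock, an addendum after it.

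The cost is one listing and its shell, from data that the protocol marks for database entry, with no new assessments. A summary of QTcF or rhythm is an optional extra and depends on whether the eCRF contains those fields.

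If the sponsor still prefers to omit the listing, the SAP should give a reason based on safety or on the data, and 2.6 should exclude protocol 10.5.3.4's ECG item explicitly.

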5.1 Imputation rules

All imputation rules were defined in previous sections of the SAP, as referenced below.

5.1.1 Study drug

See [Section 2.5.1.1](#).

5.1.2 AE date imputation

See [Section 2.8.2.1.1](#).

5.1.3 Concomitant medication date imputation

Same as AE date imputation; see [Section 2.5.2](#) for discussion of concomitant medication summaries, and [Section 2.8.2.1.1](#) for the imputation rule.

5.1.4 Prior and post antineoplastic therapies date imputation

See [Section 2.3.4](#).

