2.3.4.4 Partial-date imputation rules for prior antineoplastic therapies

The following partial-date imputation rules will apply:

Start date:

The same rule which is applied to the imputation of AE/concomitant medication start date will be used, with the exception of the imputation rule in scenario (B) of [Table 2-4](#), which will be replaced by TRTSTD-1. See [Section 2.8.2.1.1](#).

End Date:

Imputed date = min (start date of study treatment, last day of the month), if day is missing;

Imputed date = min (start date of study treatment, 31DEC), if month and day are missing.

If the end date is not missing and the imputed start date is after the end date, use the end date as the imputed start date.

If both the start date and the end date are imputed and if the imputed start date is after the imputed end date, use the imputed end date as the imputation for the start date.

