Overall response rate (ORR) is defined as the proportion of patients with best overall response (BOR) of complete response (CR), complete response with incomplete marrow recovery (CRI), or partial response (PR), as assessed by investigators per IWCLL criteria (see VAY736Y2102-CSP-Appendix 1 for details) and will be calculated based on all response evaluations. The ORR will be calculated by dose level in dose escalation and by arm in dose expansion, and overall, and will be presented along with corresponding 90% exact confidence intervals (CI). Assessments taken after the start of alternative cancer therapy will be excluded.

Time to progression (TTP) is the time from start of treatment to the date of event which is defined as the first documented progression (defined as overall disease response assessment of PD) or death due to underlying cancer. If a patient has not had an event, time to progression is censored at the date of last adequate disease assessment. Assessments taken after the start of alternative cancer therapy will be excluded.

Median TTP (in months) with corresponding 95% CI, 25th and 75th percentiles (Brookmeyer and Crowley 1982, Klein and Moeschberger 1997) and Kaplan-Meier estimated probabilities (TTP rate) with corresponding 95% CIs (Greenwood's formula, Kalbfleisch and Prentice 1980) at several time points (3, 6, 12, 18 and 24 months) will be presented. The number (%) of progressions, deaths and patients censored will also be summarized.

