2.8.2.1 Adverse events (AEs)

2.8.2.1.1 Data handling and AE date imputation rules

Adverse events will be coded using the Medical Dictionary for Regulatory Activities (MedDRA) and assessed according to the Common Terminology Criteria for Adverse Events (CTCAE) version 4.03, respectively.

The CTCAE represents a comprehensive grading system for reporting the acute and late effects of cancer treatments. CTCAE grading is by definition a 5-point scale generally corresponding to mild, moderate, severe, life threatening, and death. This grading system inherently places a value on the importance of an event, although there is not necessarily proportionality among grades (a grade 2 is not necessarily twice as bad as a grade 1).

If CTCAE grading does not exist for an adverse event, the severity of mild, moderate, severe, and life-threatening, death related to the AE corresponding respectively to Grades 1 - 5, will be used. Information about any deaths (related to an Adverse Event or not) will also be collected through a Death form.

A missing AE start date will be imputed using the following logic matrix described in [Table 2-3](#).

Table 2-3 Imputation rules for a partially missing AE start date

	AEM MISSING	AEM < TRTM	AEM = TRTM	AEM > TRTM
AEY MISSING	No imputation	No imputation	No imputation	No imputation
AEY < TRTY	(D)	(C)	(C)	(C)
AEY = TRTY	(B)	(C)	(B)	(A)
AEY > TRTY	(E)	(A)	(A)	(A)

AEM: Month AE started; AEY: Year AE started

TRTM: Month treatment started; TRTY: Year treatment started

[Table 2-4](#) is the legend to the logic matrix shown in [Table 2-3](#) and details the relationship of AE start date to study treatment start date.

Table 2-4 Imputation legend and AE/treatment start date relationship

	AE start date relationship	Imputation
(A)	After treatment start or Uncertain	MAX(01MONYYYY, TRTSTD+1)
(B)	Uncertain	TRTSTD+1
(C)	Before treatment start	15MONYYYY
(D)	Before treatment start	01JULYYYY
(E)	After treatment start	01JANYYYY

Before treatment start: Partial date indicates AE start date is prior to treatment start date.

After treatment start: Partial date indicates AE start date is after treatment start date.

Uncertain: Partial date insufficient to determine relationship of AE start date to treatment start date.

No imputation will be performed for AE end dates.

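### SAP 5.1.4 sends partial dates of post-study cancer therapy to a rule written for prior therapy; taken literally, the new therapy can be dated to study day 1 or day -1, which would void that patient's ORR and TTP data

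*SAP*

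**What the plan says.** **The cross-reference.** SAP 5.1 states that "All imputation rules were defined in previous sections of the SAP, as referenced below". Section 5.1.4, "Prior and post antineoplastic therapies date imputation", contains only a pointer to 2.3.4. The one imputation rule there is 2.3.4.4, "Partial-date imputation rules for prior antineoplastic therapies".

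**The rule.** In 2.3.4.4:
- A partial start follows the AE matrix (Tables 2-3 and 2-4), except for scenario (B), "which will be replaced by TRTSTD-1".
- A partial end is "Imputed date = min (start date of study treatment, last day of the month), if day is missing". The same cap applies, with 31 December, when the month is missing too.
- "If both the start date and the end date are imputed and if the imputed start date is after the imputed end date", the start is set to that imputed end.

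**Where the therapy start date is used.**
- SAP 2.1.1.7 takes the start of alternative cancer therapy from the post-discontinuation antineoplastic eCRF and exempts ibrutinib. It is silent on partial dates.
- SAP 2.8.1 states, once under ORR and once under TTP: "Assessments taken after the start of alternative cancer therapy will be excluded".
- SAP 5.2.4.1 closes the best-overall-response window at new therapy.
- SAP Table 5-3, situation F, default option, censors TTP at the last adequate assessment before new therapy.

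No visible item in SAP section 4 supplies a separate rule for post-study therapy.

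**The concern.** The cap at first dose is sensible for prior therapy, which must have ended by then. For therapy given after study treatment the cap always binds, so it moves the date to the wrong end of the patient's record.

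The date is not only descriptive. It decides which assessments count towards two secondary efficacy endpoints. A badly misdated switch removes assessments made before the patient changed therapy, and it does so only in patients who switched. The loss is therefore related to outcome.

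**Working it through.** The plan gives no figure to reproduce, so the check is a trace of the written rule. Let T be the date of first dose (TRTSTD).

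**Step 1, end date.** Imputed end = min(T, last day of the recorded period). For a post-study therapy that last day is on or after T, so imputed end = T in every case.

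**Step 2, start date** (Tables 2-3 and 2-4, as modified by 2.3.4.4).
- (A) Day missing, recorded month after the month of first dose: the later of the first of that month and T+1.
- (B) Recorded month is that of first dose, or only the year is known and it is the year of first dose: T-1.
- (E) Only the year is known and it is a later year: 1 January.

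**Step 3, reset.** When both dates are imputed, a start from (A) or (E) is later than T and is pulled back to T, study day 1. A start from (B) is already before T and stays at day -1.

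**Step 4, example.** T = 10-Jun-2021. C9D1 is day 8 × 28 + 1 = 225, which is 20-Jan-2022.

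| Recorded therapy dates | Imputed start | Study day |
|---|---|---|
| Sep-2022 to Dec-2022 | 10-Jun-2021 | 1 |
| 2022 only, partial end | 10-Jun-2021 | 1 |
| 2021 only, ongoing | 09-Jun-2021 | -1 |
| Sep-2022, ongoing | 01-Sep-2022 | 449 |
| 2022 only, ongoing | 01-Jan-2022 | 206 |

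The last row falls before C9D1, so that assessment would be excluded too.

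A grid gives the same result as steps 1 to 3. It used 365 first-dose dates and therapy starts every 7 days from 29 to 953 days later, with the day missing from both dates. Of 365 × 133 = 48,545 records, 48,527 landed on day 1 and 18 on day -1. This is conditional on both dates being partial and says nothing about how often that occurs.

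**Step 5, effect of a day 1 or day -1 start.** All post-baseline assessments come after the therapy start and are excluded. Best overall response becomes unknown (5.2.4.1), and 2.6.2 counts an unknown response as a non-responder in the denominator. With no post-baseline assessment left, 5.2.4.2 and Table 5-3 situation A give a censored TTP of 1 day. Suppose progression was documented on 12-Sep-2022. The true record is an event at 459 + 1 = 460 days, or 460/30.44 = 15.1 months.

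**Step 6, only the start day missing, therapy ongoing.** Assessments up to the first of the month survive, so earlier responses are kept. Progression is dropped if it falls after the first of the month in which therapy began. Let g be the days from progression to the true start. The start must then fall on day g+2 of the month or later. Averaged over calendar days, with mean month 365/12 = 30.42 days, the share is (30.42 - (g+1))/30.42.

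| g (assumed) | Share of progressions dropped |
|---|---|
| 1 day | 93% |
| 7 days | 74% |
| 14 days | 51% |
| 21 days | 28% |

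**Step 7, size for ORR.** With the planned 20 patients per arm, one lost responder is 1/20 = 5 points. For example, 10/20 = 50% (exact 90% CI 30.2 to 69.8) becomes 9/20 = 45% (25.9 to 65.3). ORR is also reported by dose level in escalation. There, a level with a single cohort of 3 to 6 patients would move by 1/6 to 1/3, or 17 to 33 points.

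**The case against.** **The link to efficacy is inferred.** SAP 2.1.1.7 takes the start date as recorded on the eCRF and does not cite 5.1.4. Neither does 2.8.1, 5.2.4.1 or Table 5-3. Imputed dates might serve listings only, and SAP section 1 places derived-variable specifications in a separate programming document that is not available here. This stands as a limit on what can be asserted. It does not clear the text: 5.1 says all imputation rules are the ones it references, so 5.1.4 is the only written handling of a partial post-study date. If it does not apply, partial dates in 2.1.1.7 have no handling at all.

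**It is a loose cross-reference that a programmer would notice.** Probably so. But the written rule is wrong for this use, and the SAP should not depend on someone departing from it.

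**Partial dates may be rare.** Follow-up visits are every 3 months (protocol 7.1.2) and missing values are queried (protocol 9.4). Day 1 needs both dates partial; day -1 needs the month missing in the year of first dose, or a switch in the month of first dose. This stands, and it limits the severity.

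**First-of-month imputation is common, and censoring at a switch is already the plan's default.** Both are true. The added harm in step 6 is only that a progression preceding the switch can be treated as following it.

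**Conclusion.** Wrong as written; moderate severity. The literal rule gives impossible start dates for post-study therapy. If those dates feed 2.1.1.7, the affected patient's ORR and TTP results are wrong: fully so for day 1 or day -1 starts, and mainly by loss of the progression event when only the day is missing.

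The size per patient in steps 5 to 7 rests on the planned arm size of 20 and on assumed gaps from progression to switch. The total effect cannot be stated, because the documents give no count of partial dates.

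A reader might infer that valid responses and progressions will be deleted and that the trial's efficacy results are biased. The documents do not support that. The path from 5.1.4 to the efficacy cut is not spelled out, and continued ibrutinib is exempt. The CR/CRi rate at C9, which 2.8.1 names as the main activity endpoint, carries no exclusion after new therapy. ORR and TTP are descriptive secondary endpoints. Nor do responders generally become non-responders when only the start day is missing, since responses before that month still count.

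**What to change.** 1. Remove post therapies from the cross-reference in 5.1.4 and keep 2.3.4.4 for prior therapy only.
2. Give post-study therapy its own rule and cite it in 2.1.1.7:
   - Partial start: the later of the first day of the recorded month or year and the day after last on-study treatment, with that last date defined in the SAP.
   - Partial end: the earlier of the last day of the recorded period and last contact or data cut-off.
   - Never use study treatment start or TRTSTD-1.
3. If only the day is missing and progression is documented in the same month, keep the progression as the event by setting the start no earlier than the day after it. This depends on the outcome, but the possible error is confined to one month.
4. Do not extend item 3 to year-only starts. A therapy recorded only as 2022 could have begun in February for another reason, with progression in November; moving the start past November would keep assessments made on the new therapy, contrary to 2.8.1. Query and list these records, and show ORR and TTP under the earliest and latest possible start as a sensitivity analysis.

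In the example, Sep-2022 to Dec-2022 with progression on 12-Sep-2022 becomes 13-Sep-2022 to 31-Dec-2022 (if last contact and cut-off are no earlier), and the event at day 460 is kept.

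Cost: a few lines of SAP text and a small amount of programming, ideally before database lock. Apart from answers to the queries, no new data are needed.
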